3.8 Termination of the study

The study may be stopped if, in the judgment of AstraZeneca, trial subjects are placed at undue risk because of clinically significant findings that:

- meet individual stopping criteria or are otherwise considered significant
- are assessed as causally related to study drug,
- are not considered to be consistent with continuation of the study

Regardless of the reason for termination, all data available for the subject at the time of termination of follow-up must be recorded in the CRF. All reasons for discontinuation of treatment must be documented.

In terminating the study, the Sponsor will ensure that adequate consideration is given to the protection of the subjects' interests.

4. STUDY PLAN AND TIMING OF PROCEDURES

Table 1 Study Plan

Visit	Screening	Treatment Period (further treatment cycles as per Cycle 7)								Follow-up Period			For details see Protocol Section
	1	2	3	4	5	6	7-9	10+	Treatment Discontinuation	28-day follow-up	Progression follow-up	Survival follow-up	
Cycle ^a / Day		C1 D1	C1 D8	C1 D15	C2 D1	C3 D1	C4-6 D1	C7 ^b + D1	NA	NA	NA	NA	
Day	-28	1	8	15	22	43	64-106	127+	NA	NA	NA	NA	
Window (days)	NA	0	±2	±2	±7	±7	±7	±7	NA	±7	±7	±7	SECTION:
Informed consent ^c	X												3.3 & 4.1
Submit mandatory tumour tissue sample for mutation analysis ^d	X												4.1 & 5.6
Submit tumour tissue for diagnostic development (optional) ^e	X												4.1, 5.6 & 5.6.3.2
Optional tumour biopsy for exploratory research									X				5.6
Archival tumour tissue ^f	X												5.6
Demography & baseline characteristics	X												4.1
Medical/surgical history	X												4.1
Inclusion/exclusion criteria	X												3
Physical examination, including weight	X	X ^g			X	X	X	X	X				5.2.3 & 5.2.6.2

Table 1 Study Plan

Visit	Screening	Treatment Period (further treatment cycles as per Cycle 7)								Follow-up Period			For details see Protocol Section
	1	2	3	4	5	6	7-9	10+	Treatment Discontinuation	28-day follow-up	Progression follow-up	Survival follow-up	
Cycle ^a / Day		C1 D1	C1 D8	C1 D15	C2 D1	C3 D1	C4-6 D1	C7 ^b + D1	NA	NA	NA	NA	
Day	-28	1	8	15	22	43	64-106	127+	NA	NA	NA	NA	
Window (days)	NA	0	±2	±2	±7	±7	±7	±7	NA	±7	±7	±7	SECTION:
Height	X												5.2.6.2
WHO Performance status	X	X			X	X	X	X	X				4.1
Pregnancy test (pre-menaopausal females only)	X												5.2.1
Ophthalmologic assessment	X	← as clinically indicated →											5.2.7.1
Vital signs ^g	X	X	X	X	X	X	X	X	X				5.2.6
Clinical chemistry/ Haematology/Urinalysis ^g	X ^h	X	X	X	X	X	X	X	X				5.2.1
Digital ECG	X	X	X ^g	X ^g	X ^g	X	X	X	X				5.2.4
Echocardiogram/MUGA	X		← every 12 weeks relative to first dose →										5.2.5
PK blood sample (including metabolites)		X			X	X							5.4
Plasma sample for ctDNA ^g	X ⁱ	X	X	X	X	X	X	← every 6 weeks in line with RECIST assessments ^j →					4.3.3 & 5.6.2
Optional genetic consent and sample	X ^k												5.5

Table 1 Study Plan

Visit	Screening	Treatment Period (further treatment cycles as per Cycle 7)								Follow-up Period			For details see Protocol Section
	1	2	3	4	5	6	7-9	10+	Treatment Discontinuation	28-day follow-up	Progression follow-up	Survival follow-up	
Cycle ^a / Day		C1 D1	C1 D8	C1 D15	C2 D1	C3 D1	C4-6 D1	C7 ^b + D1	NA	NA	NA	NA	
Day	-28	1	8	15	22	43	64-106	127+	NA	NA	NA	NA	
Window (days)	NA	0	±2	±2	±7	±7	±7	±7	NA	±7	±7	±7	
Optional CSF sample					X (once only) ¹								SECTION: 5.5.2
Tumour assessments (RECIST v1.1) ^m	X	← every 6 weeks relative to first dose until disease progression →										4.2 & 5.1.1	
EORTC QLQ-C30 and EQ-5D-5L (by electronic device)		X ^g	← every 6 weeks relative to first dose →					X		X ⁿ	X ⁿ	5.3.2.1 & 5.3.2.2	
EORTC QLQ LC13 (by electronic device)		X ^g	← weekly relative to first dose →		← every 3 weeks relative to first dose →			X		X ^o	X ^o	5.3.2.1	
PRO-CTCAE (by electronic device) ^p		X ^g	← weekly for first 18 weeks of treatment →				X ^q	X		X ^o	X ^o	5.3.2.3	
Healthcare Resource Use		← →										5.3.2.5	
Dispense study medication		X			X	X	X	X					3.3 & 7.2
Dose with AZD9291		← Daily dosing →											7.2
Concomitant medication & procedures		← →										7.7	
Adverse events		← →										X ^r	6.3 & 6.4

Table 1 Study Plan

Visit	Screening	Treatment Period (further treatment cycles as per Cycle 7)								Follow-up Period			For details see Protocol Section
	1	2	3	4	5	6	7-9	10+	Treatment Discontinuation	28-day follow-up	Progression follow-up	Survival follow-up	
Cycle ^a / Day		C1 D1	C1 D8	C1 D15	C2 D1	C3 D1	C4-6 D1	C7 ^b + D1	NA	NA	NA	NA	
Day	-28	1	8	15	22	43	64-106	127+	NA	NA	NA	NA	
Window (days)	NA	0	±2	±2	±7	±7	±7	±7	NA	±7	±7	±7	SECTION:
Survival Status												X ^s	4.3.4
Anti-cancer treatment											X	X ^s	4.3.3, 4.3.4
Subsequent response /progression data												X ^t	5.8

a A cycle is defined as 21-day treatment period.

b Visit schedule changes after Cycle 7 Day 1 from every 21 days (3 weeks) to every 42 days (6 weeks).

c Consent may be taken prior to 28-day window if required.

d Taken following progression on the latest line of therapy.

e The optional second tumour tissue sample can be taken as part of the same procedure as the mandatory screening biopsy for mutation analysis.

f Archival tumour sample only to be submitted after T790M positive status confirmed by central testing. Not required for T790M negative patients.

g To be completed pre-dose.

h If screening assessments have been performed within 14 days prior to starting study treatment they do not have to be repeated on Visit 2 if the patient's condition has not changed.

i To be taken at the same time as the screening biopsy is taken or prior to mutation screening. All plasma samples are required by AstraZeneca, regardless of the outcome of the mutation screening.

j Collect every 6 weeks up to and including progression (corresponding with the RECIST assessments – and continuing after treatment discontinuation in absence of disease progression).

k If for any reason the sample is not drawn prior to first dose it may be taken at any visit until the last study visit.

l To be obtained at one time point at any time from Cycle 2 Day 1 onwards

m At least one lesion, not previously irradiated and not chosen for biopsy during the study screening period, that can be accurately measured.

- n Assess every 6 weeks relative to first dose until end of study (including survival follow-up period) and at the time of progression.
- o Assess every 3 weeks relative to first dose until end of study (including survival follow-up period) and at the time of progression.
- p PRO-CTCAE will only be administered in those countries where a linguistically validated version exists.
- q Assessed at Cycle 7 Day 1 then every 3 weeks relative to first dose thereafter until end of study (including survival follow-up period) and at the time of progression.
- r Following AZD9291 discontinuation, SAEs considered related to study procedures should continue to be collected until disease progression.
- s Survival status including anti-cancer treatment to be performed every 6 weeks (relative to first dose) following disease progression or withdrawal from treatment.
- t Record subsequent response/progression data every 6 weeks until first confirmed disease progression on a subsequent treatment.

4.1 Screening period

It is recommended the screening assessments be performed in a stepwise process beginning with the confirmation of T790M mutation status as determined by the designated central laboratory. However, screening assessments may be done in parallel to the T790M mutation assessment, as appropriate. Procedures will be performed according to the Study Plan ([Table 1](#)).

At screening, consenting subjects are assessed to ensure that they meet eligibility criteria. Subjects who do not meet these criteria must not be enrolled in the study. Demographic data and other characteristics will be recorded and will include date of birth or age, gender, smoking history, race and/or ethnicity according to local regulations.

Patients will be considered in screening period until all Visit 1 assessments are completed and eligibility is confirmed. Patients will be considered enrolled and in the treatment period once AZD9291 therapy has been initiated.

Mandatory screening tumour biopsy sample for mutation analysis:

Tumour sample must be formalin fixed and paraffin embedded (FFPE) and must be biopsied following progression on the latest line of therapy. Samples may be collected from primary or metastatic tumour deposits. Sites should ship the FFPE tumour sample to the testing laboratory as soon as it is available. Blocks must be provided wherever possible. If this is not possible, 20 slides of freshly prepared unstained 5-micron sections from this screening tumour block may be provided. See [Section 5.6](#).

The mandatory screening tumour biopsy must not be taken from a previously irradiated lesion or the lesion(s) selected for Inclusion criterion number 9 (biopsy). This biopsy sample is not subject to the 28-day screening window; if tissue is already available from a biopsy taken since confirmation of disease progression on the most recent treatment regimen then there is no need for a further biopsy as this sample can be submitted for T790M mutation status. If the first biopsy is not confirmed as T790M mutation positive (i.e., due to test failure or if tests negative for the T790M mutation) a further biopsy sample may be submitted for central testing.

Optional second tissue sample for diagnostic development:

The optional second tissue sample (FFPE) may be provided to facilitate diagnostic development and pre-market approval of the diagnostic test. This should be obtained at the same time and as part of the same procedure as the mandatory screening biopsy.

Written informed consent/Assignment of subject enrolment number:

Each potential subject will provide informed consent prior to starting any study specific procedures (see [Section 10](#) of this Clinical Study Protocol for Ethics and Regulatory Requirements). All subjects will be required to provide consent to supply a new tumour biopsy sample entry into this study. This consent is included in the main subject informed

consent form. However, please note that patients are asked to provide separate consent for provision of optional tumour biopsy samples, if willing (see Section 5.6).

Additionally, patients will be given the option to consent to the host pharmacogenetics research component of the study in a separate Informed Consent Form (ICF).

Once consent has been signed, the PI or delegate, will contact IVRS/IWRS to have the subject assigned a unique enrolment number.

WHO Performance Status:

Performance status will be assessed at the visits indicated in the Study Plan (see [Table 1](#)) according to WHO criteria as follows:

- 0 = Fully active, able to carry out all pre-disease activities without restrictions
- 1 = Restricted in physically strenuous activity but ambulatory and able to carry out work of a light or sedentary nature eg, light housework, office work
- 2 = Ambulatory and capable of self-care, but unable to carry out any work activities. Up and about more than 50% of waking hours
- 3 = Capable of only limited self-care, confined to bed or chair more than 50% of waking hours
- 4 = Completely disabled, cannot carry on self-care, totally confined to bed or chair

4.2 Treatment period

A cycle of treatment is defined as 21 days of once daily AZD9291 treatment. After Cycle 7 Day 1, the duration between study visits will change from every 21 days (3 weeks) to every 42 days (6 weeks).

If a patient continues to receive treatment with AZD9291 beyond RECIST 1.1 defined progression they must continue to follow the Treatment visit schedule and assessments excluding study specific RECIST 1.1 assessments.

Descriptions of the procedures for this period are included in the Study Plan ([Table 1](#)).

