The study was designed to estimate the response rates in patients with T790M mutation positive advanced NSCLC who have progressed on or after EGFR-TKI treatment. ORR will be estimated with 95% exact CIs. With 175 patients the precision of the estimation of ORR in the overall study population will be within +/-8% (e.g. ORR 40%, 95% CI 33.0%, 47.4%). The ORR will also be presented by patient cohort: patients who received previous TKI only; patients who received a TKI and a platinum-based doublet chemotherapy (patients may have also received additional lines of treatment).

Secondary efficacy variables include: DoR, DCR, PFS (according to RECIST 1.1 as assessed by ICR); HRQoL and symptoms; overall survival (OS).

For the primary analysis, ORR will be based on ICR defined visit responses. The imaging scans will be reviewed by two independent radiologists blinded to individual patient data using RECIST 1.1 criteria and will be adjudicated if required. For each patient, the ICR will define the overall visit response data and the relevant scan dates for each time point (i.e. for visits where response or progression is/is not identified). Endpoints (ORR, DoR, DCR, PFS) will be derived from the overall visit response data and the scan dates. Sensitivity analyses of ORR, DoR, DCR and PFS from the investigators assessment will also be performed. The concordance between ORR as assessed by ICR and by investigator will be presented.

The data cut-off for the primary analysis of ORR will take place approximately 3 months after the last subject has been enrolled, to allow opportunity for all patients to complete two RECIST follow-up assessments. At this time, DoR and safety/tolerability will also be summarised. The primary analysis CSR will report the analysis of ORR supported by DoR, and safety and tolerability data.

The full CSR will report the analysis of all primary and secondary endpoints (including updated ORR and DoR, DCR, tumour shrinkage, PFS, OS, Safety, HRQoL, QTc and PK) and summarise the exploratory endpoint of patient reported adverse events (PRO-CTCAE). The data cut-off for this analysis will take place approximately 8 months after the last subject has been enrolled, to allow responding patients to have a DoR greater than 6 months.

Clinical Study Protocol
Drug Substance AZD9291
Study Code D5160C00002
Edition Number 1
Date 26 February 2014

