5.1 Efficacy assessments

5.1.1 RECIST 1.1

All imaging assessments including unscheduled visit scans should be collected on an ongoing basis and sent to an AstraZeneca (AZ) appointed Clinical Research Organisation (CRO) to enable independent central analyses.

For both Independent Central Review (ICR) and investigator review RECIST 1.1 criteria will be used to assess each patient's tumour response to treatment and allow calculation of ORR, PFS, DCR, DoR, and assess tumour shrinkage. The RECIST 1.1 guidelines for measurable, non-measurable, target and non-target lesions and the objective tumour response criteria [CR (complete response), PR (partial response), SD (stable disease) or PD (progression of disease)] are presented in [Appendix D](#). For ORR, a visit response of CR or PR must be confirmed by a later scan conducted at least 4 weeks after the initial response is observed. See [Section 4](#) for considerations related to RECIST 1.1 assessments.

The methods used at baseline for assessment of tumour burden [CT or MRI scans of chest and abdomen (including liver and adrenal glands)] must be used at each subsequent follow-up assessment. Any other areas of disease involvement should be additionally investigated based on the signs and symptoms of individual patients. CT/MRI scan of the brain should be performed in patients with known or suspected brain metastases. The baseline assessment should be performed within 28 days of treatment start. Assessments to be performed every 6 weeks relative to first dose until objective disease progression. It is important to follow the assessment schedule as closely as possible. If scans are performed outside of the scheduled visit \pm 1 week window interval and the patient has not progressed, every attempt should be

made to perform the subsequent scans at their scheduled time points. Any other sites at which new disease is suspected should also be appropriately imaged.

If the investigator is in doubt as to whether progression has occurred, particularly with response to non-target lesions (NTLs) or the appearance of a new lesion, it is advisable to continue treatment until the next scheduled assessment or sooner if clinically indicated and reassess the patient's status. If repeat scans confirm progression, then the date of the initial scan should be declared as the date of progression.

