5.1.2 RECIST 1.1 Independent Central Review assessment

The primary analysis for this study will be based on ORR using Independent Central Review (ICR) of patients with measurable disease at baseline as assessed by the ICR, according to RECIST 1.1. All scans from all patients (with both progressive and non-progressive disease by investigator assessment), used in the assessment of tumours using RECIST 1.1 will be conducted. All imaging assessments including unscheduled visit scans will be collected on an ongoing basis and sent to an AstraZeneca appointed CRO to enable central analysis. Results of this independent review will not be communicated to Investigators and the management of patients will be based solely upon the results of the RECIST 1.1 assessment conducted by the Investigator.

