ORR rate is defined as the number (%) of subjects with measurable disease with at least one visit response of CR or PR that is confirmed at least 4 weeks later (according to ICR for the primary analysis). Data obtained up until progression, or last evaluable assessment in the absence of progression, will be included in the assessment of RR. However, any complete response or partial response which occurred after a further anticancer therapy was received will not be included in numerator of the ORR calculation.

In the case where a subject has two non-consecutive visit responses of PR, then, as long as the time between the 2 visits of PR is greater than 4 weeks and there is no PD between the PR visits, the subject will be defined as a responder. Similarly, if a subject has visit responses of CR, NE, CR, then, as long as the time between the 2 visits of CR is greater than 4 weeks, then a best response of CR will be assigned.

Duration of Response (DoR)

Duration of response will be defined as the time from the date of first documented response, (that is subsequently confirmed) until date of documented progression or death in the absence of disease progression, the end of response should coincide with the date of progression or death from any cause used for the PFS endpoint. The time of the initial response will be defined as the latest of the dates contributing towards the first visit response of PR or CR. If the response is not confirmed, it will not be included.

If a subject does not progress following a response, then their duration of response will use the PFS censoring time.

Disease control rate (DCR)

Disease control rate is defined as the percentage of patients who have a BoR of CR or PR or SD.

Tumour Shrinkage

Tumour shrinkage will be assessed using RECIST tumour response. The absolute change and percentage change from baseline in sum of tumour size at each assessment will be calculated. The best change in tumour size will include all assessments prior to progression or start of subsequent anti-cancer therapy.

Progression Free Survival (PFS)

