8.9.2 Analysis of the secondary variable(s)

Duration of response

Duration of response in responding patients will be summarised and the number (%) of responding patients with a duration of response >3; >6; >9; >12 months will be presented. A

Kaplan Meier plot and median duration of response with 95% CI (calculated from the Kaplan Meier plot) will be presented. DCR will be summarised. DoR and DCR will be presented based on the ICR, and as a sensitivity analysis they will be present based on the investigator assessment.

Tumour shrinkage

The best absolute change in target lesion tumour size from baseline and percentage change in target lesion tumour size from baseline will be summarized using descriptive statistics and presented at each timepoint.

Tumour size will also be presented graphically using waterfall plots, to present each patient's best percentage change in tumour size as a separate bar, with the bars ordered from the largest increase to the largest decrease. Reference lines at the +20% and -30% change in tumour size levels will be added to the plots, which correspond with the definitions of progression and 'complete or partial' response respectively.

The mean and median best change from baseline in tumour size will be summarized. This will also be summarised for week 6 and week 12 data.

To assess the depth of tumour shrinkage, the proportion of patients who achieve >30%, >50% and >75% reduction in target lesions will be summarised descriptively.

Tumour shrinkage will be presented based on the primary reader ICR data, and as a sensitivity analysis they will be present based on the investigator assessment.

Progression Free Survival (PFS)

PFS will be displayed using a Kaplan-Meier plot. The number events, median (calculated from the Kaplan Meier plot), and the proportion of patients without an event at 6, 12 and 18 months summarised. PFS will be presented based on the ICR assessments, and as a sensitivity analysis PFS will be presented based on the investigator assessment.

Overall Survival (OS)

When there is sufficient data (>20 events), OS will be displayed using a Kaplan-Meier plot. The number events, median (calculated from the Kaplan Meier plot), and the proportion of patients without an event at 6, 12 and 18 months will be summarised.

As appropriate, summaries of the number and percentage of patients who have died, are still in survival follow-up, are lost to follow-up and have withdrawn consent will be presented.

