8.4 Outcome measures for analyses

Previous text:

Progression Free Survival (PFS)

PFS is defined as the time from enrolment until the date of objective disease progression or death (by any cause in the absence of progression) regardless of whether the patient withdraws from study therapy or receives another anti-cancer therapy prior to progression. Patients who have not progressed or died at the time of analysis will be censored at the time of the latest date of assessment from their last evaluable RECIST assessment.

Revised text:

Progression Free Survival (PFS)

PFS is defined as the time from **date of first dose** until the date of objective disease progression or death (by any cause in the absence of progression) regardless of whether the patient withdraws from study therapy or receives another anti-cancer therapy prior to

progression. Patients who have not progressed or died at the time of analysis will be censored at the time of the latest date of assessment from their last evaluable RECIST assessment.

Section of protocol affected:

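### Scanning stops at the investigator's progression call while the main PFS and DoR analyses use blinded central review, so informative censoring may make the central PFS and DoR look too good

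*Supplement*

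**What the plan says.** The reference is protocol edition 1 as changed by Amendments 1 and 2; neither amendment alters the rules below.

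- **When scans stop.** Section 5.1.1: "Assessments to be performed every 6 weeks relative to first dose until objective disease progression". Section 4.2, for patients kept on AZD9291 after progression: "they must continue to follow the Treatment visit schedule and assessments excluding study specific RECIST 1.1 assessments". Section 4.3.3 continues scans off treatment only for patients who stopped for a reason other than progression.
- **Whose call it is.** Section 5.1.2: "Results of this independent review will not be communicated to Investigators", and "management of patients will be based solely upon the results of the RECIST 1.1 assessment conducted by the Investigator". The synopsis has the scans "reviewed by two independent radiologists blinded to individual patient data using RECIST 1.1 criteria".
- **Which reading is analysed.** Section 8.9.2: "PFS will be presented based on the ICR assessments, and as a sensitivity analysis PFS will be presented based on the investigator assessment". DoR is handled in the same way.
- **Censoring.** Section 8.4, as revised by Amendment 2: "Patients who have not progressed or died at the time of analysis will be censored" at their last evaluable RECIST assessment. A progression or death that comes after three or more missed assessments is censored back to that assessment. For DoR: "If a subject does not progress following a response, then their duration of response will use the PFS censoring time".
- **A conflicting stop rule.** Appendix D Section 4.1 runs the 6-weekly scans until study treatment is discontinued or consent is withdrawn, not until progression.

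**The concern.** Consider a patient whom the investigator calls progressed on a scan that the ICR does not call progressed. Sections 4.2 and 5.1.1 require no further study scan, so the ICR may never see the progression it would have called later. The patient is then censored at the scan on which somebody judged the disease to be worsening.

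Kaplan-Meier assumes that a censored patient has the same future risk as those still under observation. If investigator progression is a warning of ICR progression, that assumption fails in the favourable direction.

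The medians, the PFS proportions at 6, 12 and 18 months and the counts of responders with DoR beyond 3, 6, 9 and 12 months are all read from these dates. There is no control arm to share the bias. Amendment 2 also brings all efficacy endpoints into the primary report. The planned ICR-investigator concordance covers ORR only, so the number of patients affected would not be visible.

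**Working it through.** The plan gives no median, event count or discordance rate for PFS or DoR, so there is no stated figure to reproduce. The size has to be shown over assumed ranges.

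**Inputs from the documents.** Scans every 6 weeks, W = 6/4.345 = 1.381 months. Death counts as an event if it precedes three missed assessments, a window of 3 × 1.381 = 4.14 months. Section 1.4 puts median survival at about 10 to 16 months in this setting.

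**Assumed.** Exponential ICR PFS with a true median of 9 months (6 and 12 as checks). A share d = 10%, 20% or 30% of patients is called progressed by the investigator one or two scans before the ICR would call it. Median survival after progression is 10 months (5 and 16 as checks). Data cut-off falls 12 to 24 months after entry.

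**Step 1: reference with scanning continued to ICR progression.** The last scan before 12 months is the eighth, at 8 × 1.381 = 11.05 months, so PFS is 0.5^(11.05/9) = 42.7%. The scan-based median is the seventh scan, 7 × 1.381 = 9.67 months. Simulation gives 42.4–42.7% and 9.7 months.

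**Step 2: scanning stops at the investigator's call, deaths ignored.** The chance of progression per interval is p = 1 − 0.5^(1.381/9) = 0.1009. With a one-scan lead, the Kaplan-Meier hazard from the second scan on is h = (1 − d)p/(1 − dp). At the first scan it stays p, because no earlier scan exists. Reported 12-month PFS is (1 − p)(1 − h)^7:

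| d | h | 12-month PFS |
|---|---|---|
| 10% | 0.0917 | 45.8% |
| 20% | 0.0824 | 49.3% |
| 30% | 0.0728 | 53.0% |

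**Step 3: how many affected patients the death rule recovers.** With a one-scan lead, ICR progression falls on average half an interval after the stop, leaving about 2.5 × 1.381 = 3.45 months of the window: 1 − 0.5^(3.45/10) = 21%. With a two-scan lead, 1.5 × 1.381 = 2.07 months are left: 1 − 0.5^(2.07/10) = 13%. The simulation, which also applies the data cut-off, gives about 20% and 12%. With a one-scan lead and survival medians of 16 and 5 months it gives 13% and 35%. The rule softens the effect but does not remove it.

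**Step 4: simulation with the death rule** (400,000 patients per scenario, true median 9 months):

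| d | Reported 12-month PFS, lead 1 / lead 2 | Reported median, months | 12-month PFS if investigator progression counts as an event, lead 1 / lead 2 |
|---|---|---|---|
| 10% | 45.0% / 44.4% | 9.9 / 9.8 | 42.3% / 41.8% |
| 20% | 47.4% / 46.6% | 11.0 / 10.9 | 41.7% / 41.1% |
| 30% | 50.0% / 48.7% | 12.0 / 11.2 | 41.2% / 40.1% |

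Over true medians of 6 to 12 months the overstatement at 12 months is about 1.7 to 7.5 percentage points. The median moves in steps of the scan interval, so it barely shifts at 10% and then jumps. The landmark rate is the steadier measure.

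**Step 5: investigator calls unrelated to later ICR progression.** With 7% to 25% of patients stopped at random, 12-month PFS stays at 42.7%. It moves by 0 to −0.5 points once early deaths count.

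**The case against.** The other side has five arguments.

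1. **Investigator-based PFS and DoR are already planned** (Sections 8.9.2 and 8.9.5). In the model above, where the investigator is never later than the ICR, that analysis is the same as counting investigator progression as an event. This stands, and it gives useful context. It is not a guaranteed bound, because the ICR may progress some patients before the investigator does and the investigator analysis gives those patients the later date. It also does not show how many patients were affected.
2. **The ICR receives every scan**, including unscheduled ones (Sections 5.1.1 and 8.4). Investigators in doubt are told to rescan and, if progression is confirmed, to backdate it (Section 5.1.1; Appendix D Section 4.4). This stands too. A reader might infer that the ICR can never record a later progression; that is too strong. But nothing in Sections 4.2 or 5.1.1 requires a scan after a firm investigator call.
3. **Appendix D Section 4.1 would keep scans going** for patients treated beyond progression. It conflicts with Sections 4.2 and 5.1.1, so it cannot be relied on as a safeguard until the texts are reconciled.
4. **A lead of one or two scans for every discordant patient is close to the worst case.** This is fair; the figures show a range under assumptions and are not a forecast.
5. **The SAP and the ICR Charter are not among the documents supplied** and may already hold such an analysis. The point is therefore the interaction of the protocol's own scanning and censoring rules, with the remedy to be checked against the SAP.

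**Conclusion.** The concern holds in a qualified form. The protocol's rules censor patients at an investigator progression that the ICR does not share, apart from those who die before three missed assessments. ICR PFS and DoR may then be overstated. Under the stated assumptions 12-month PFS of about 42.5% becomes about 45%, 47% or 49% at 10%, 20% or 30% discordance, and the effect is about zero if investigator calls do not predict ICR progression. The simulation covers PFS only; DoR inherits the same censoring dates, so the same direction is expected, but its size was not computed.

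Two stronger readings are not supported. One is that ICR PFS and DoR are certainly biased upward: that depends on a discordance rate and a predictive link which the documents do not give. The other is that the primary ORR is compromised. A response first seen by the ICR at the scan where the investigator calls progression could lose its confirmatory scan, but that would lower ORR and has not been quantified. ORR is largely untouched. PFS and DoR are secondary and descriptive, so no test or sample size is affected.

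**What to change.** 1. **Add one sensitivity analysis beside the main ICR PFS and DoR.** Count as an event, at its date, any investigator progression not called by the ICR after which scanning stopped. Report the number of such patients. Each of these dates is no later than the ICR date that continued scanning would have given, so, sampling error aside, the analysis gives a lower bound that neither planned analysis guarantees. If the calls are informative, it and the main analysis bracket the curve with full follow-up: 40.1–42.3% and 44.4–50.0% around about 42.5% in Step 4.
2. **Reconcile Section 4.2 with Appendix D Section 4.1** on when RECIST scans stop for patients who stay on treatment.
3. **State that the existing rule sending all scans to the ICR covers any scan taken after investigator progression.**

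The cost is one extra table per endpoint and some clarified wording. No scans are added by items 1 and 3. The small downside is that a less favourable PFS and DoR figure appears beside the main one.
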